6.1.1.1.3 ASSIST PROCEDURES

ASSIST, an integral stimulation-based CAS treatment based on clinical insights and principles of motor learning (Maas et al., 2008; Schmidt et al., 2018) and neuroplasticity (Kleim & Jones, 2008; Ludlow et al., 2008) (**Table 1**), targets speech accuracy with systematic, adaptive practice on meaningful targets (words and phrases). ASSIST shares features with other motor-based CAS treatments but differs in its specific operationalization of target selection (the “what”) and systematic adaptive practice (the “how”).

Table 1. Principles of neuroplasticity and motor learning in ASSIST. FB = feedback; KR = knowledge of results; KP = of performance.

Principle	Pre-Practice	Practice
Salience	Functionally relevant targets	
Amount	16 hrs of ASSIST; 4 utterances/session	
Attention	Focus on sound & movement	
Variability	Targets embedded in 3 different frames	
	Constant prosody	Variable prosody
Schedule	Blocked	Random
Main FB type	KP	KR
FB timing	Immediate	Delayed (2-3 sec.)
FB frequency	100%	Reduced (fading)

The “What” of ASSIST. Children practice *targets* embedded in different *frames*. Targets: Each child has a set of 30 words/phrases that are *personally meaningful* (to boost motivation and carryover potential) and *within the child’s optimal challenge range*²⁴¹ (to boost motivation and expectancies through success and increase task attention by minimizing frustration) based on phonetic inventory and baseline accuracy. For Study 3 (Lexicality), we also create 30 corresponding *nonwords* by changing a stressed

vowel (and 0+ other sounds), maintaining stress and complexity (e.g., *banana – banoono*). In any session, children practice only 4 targets to maximize practice amount for those targets. **Frames:** Targets are embedded in 3 *frames* (target + frame = *utterance*) to bolster communicative relevance, practice variability, sequencing/prosodic skills, and engage language to boost a weak link between language and speech motor planning (Shriberg et al., 2012). Frames are real words (*hi mom*) or sounds (*mommy*), designed to be functional and achievable, and differ in complexity (Jakielski, 2016) to create systematic step-up/down options.

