The “How” of ASSIST. ASSIST is designed to facilitate both in-session performance and learning (Kantak & Winstein, 2012; Lai et al., 2000; McIlwaine et al., 2010; Maas et al., 2008; Rosenbek et al., 1974; Schmidt et al., 2018). Sessions are divided into *Pre-Practice* and *Practice*. Mastered utterances move to *Maintenance*.

Pre-Practice: Pre-Practice prepares the child to take advantage of Practice by ensuring motivation and showing that the utterance is within reach (with maximal cueing if needed). Pre-Practice is designed to facilitate in-session improvement and establish motor patterns. The SLP elicits utterances via integral stimulation in blocks of up to 5 attempts, providing immediate feedback and cues needed; blocks are randomized. Once an utterance is produced correctly, it will not be elicited further; Pre-Practice ends after 1 accurate response for each utterance or 15 minutes.

Practice: Practice provides as many opportunities as possible to gain experience with assembling and producing utterance motor plans. In 4-minute *Practice Runs* children engage in intensive structured speech motor practice supported by SLP cues and feedback in ‘test-teach-retest’ sequences called *Teaching Episodes* (TE). In ‘test’ and ‘retest’ phases, the SLP elicits utterances and provides KR feedback; during the ‘teach’ phase, the SLP can provide KP feedback and support (e.g., tactile cues; slow rate) to elicit 2 additional attempts. Practice is systematically adapted to the child’s in-session performance, by varying (a) elicitation method (immediate and delayed imitation, independent production), (b) frame and (c) target, based on operationalized step-up/step-down criteria. Utterances mastered in independent production are moved to Maintenance. When all frames for a target are mastered, a new target is introduced.

Maintenance. Mastered utterances are elicited in Independent Production twice (in random order) at the start of each second session; if accuracy drops to 0%, the utterance is moved back to Practice.

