- (5) We use blinded statistical analysis. [name] (biostatistician) does not know group (Immediate or Delayed) or condition status (Simple/Complex, Word/Nonword, Massed/Distributed) and does not interact with the children or families. There is no planned unblinding of the statistician until after completion of final analysis. Inadvertent unblinding is logged.
- (6) We use blinded camp staff. Camp staff is blinded to a child's condition and targets (blinding to phase is not possible as camp staff is responsible for bringing children to and from their individual sessions). There is no planned unblinding of camp staff. Inadvertent unblinding is logged.
- (7) We adopt equipoise in all communication about the study, including in lab meetings, training of research personnel (including treating SLPs), and interactions with children and parents. For each study, we present both conditions as potentially beneficial, never referring to any condition as "no treatment" or "optimal treatment". They will simply be referred to by their condition (e.g., Simple vs. Complex, Individual vs. Group activities). This will minimize potential bias on the part of SLPs, children, and parents (who complete ratings of intelligibility and communicative participation).
- (8) Parents are not informed of their child's assigned phase (Immediate or Delayed), condition (Simple/Complex, Word/Nonword, Massed/Distributed), or targets, to minimize placebo effects on caregiver-reported outcome measures. Parents do not observe treatment sessions and are thus not aware of which items are being treated. Parents may discover this information from their children. Follow final data collection (T3), families report whether they knew their child's phase and condition, and are informed of the actual allocation. Inadvertent unblinding is logged.
- (9) We use the same clinicians across conditions in each recruitment cycle to control for clinician confounds. Each clinician will treat an equal number of children in each condition.
- (10) Treatment fidelity will be facilitated by a manualized protocol, extensive training including video review and role play, "hard-coding" in-session decision on session tracking sheets, and real-time observation and daily team debrief discussions (see **Section 6.2, Fidelity**). Independent research assistants also review randomly selected videos of treatment sessions for adherence to protocol.
- (11) We create target sets before randomization to avoid bias.

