8.1.2 DATA COLLECTION & STUDY ENDPOINTS

Data is collected by trained Data Collectors blinded to a child's treatment status, condition, and targets.

Primary efficacy outcome endpoint:

- Perceptual accuracy of treated items, judged by blinded research assistants from audio recordings. Children repeat a list of words and nonwords after a pre-recorded model (played over speakers). These speech samples serve as the basis for the primary outcome measure. Three Data Analysts (different from Data Collectors) use the three-way perceptual scoring system (e.g., Maas et al., 2012; Strand et al., 2006) to score accuracy of children's productions. Data Analysts are blinded to a child's treatment status, condition, and targets. The three-way scoring system assigns 2 points for completely correct responses, 1 point for responses with one minor error (operationally defined), and 0 points for a major error (operationally defined) or multiple errors. Scoring reliability is assessed using intra-class correlations (ICC) (single-rater two-way random effects model for absolute agreement; Hallgren, 2012; Koo & Li, 2016). Mean across analysts will be used in analysis.

Secondary efficacy outcome endpoints:

- (SE-1) Perceptual accuracy of the full 30-item set of potential targets, judged by blinded data analysts from audio recordings. Children repeat a list of words and nonwords after a prerecorded model (played over speakers). These speech samples serve as the basis for this outcome measure. Three Data Analysts (different from Data Collectors) use the three-way perceptual scoring system (e.g., Maas et al., 2012; Strand et al., 2006) to score accuracy of children's productions. Data Analysts are blinded to a child's treatment status, condition, and targets. The three-way scoring system assigns 2 points for completely correct responses, 1 point for responses with one minor error (operationally defined), and 0 points for a major error or multiple errors. Scoring reliability is assessed using intra-class correlations (ICC) (single-rater two-way random effects model for absolute agreement; Hallgren, 2012; Koo & Li, 2016). Mean across analysts will be used in analysis.

- (SE-2) ICS: Parent rating of their child's intelligibility in context, using the Intelligibility in Context Scale (ICS; McLeod et al., 2012, 2015). The ICS is completed by the same parent at each time point to control for differences between parents' perspectives.

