9.4.2 ANALYSIS OF THE PRIMARY ENDPOINT(S)

The primary endpoint measure is change score from 1 week pre to 1 week post treatment for the populations described above in **Section 9.3, Populations for Analyses**. For perceptual accuracy, at least two independent data analysts (blinded to timepoint, treatment status, condition, and targets) score each target on an ordinal 3-point scale. Mean across the data analysts for each target is then used to compute the mean across treated targets (primary endpoint) and across the full 30-item target set (secondary endpoint 1) for each timepoint (T1, T2, T3). Means are converted to percentage accuracy by dividing means by 2. Finally, difference scores are then computed by subtracting the relevant pre-treatment timepoint from the relevant post-treatment timepoint. These change scores are the primary endpoint variable entered into the analyses described below and will be reported as means with standard error.

To address the effect of ASSIST (the *ASSIST Hypothesis*, Study 1), independent two-sample t-tests will be used to compare change scores (T2 – T1) between the Immediate ASSIST group and the No ASSIST delayed control group (combined sample across Cycles 1 and 2). A separate linear model will be fitted by adjusting for potential effect of study (Cycle 1/Cycle 2) to re-assess the initial efficacy of ASSIST.

To address the effect of complexity (*Simplicity vs. Complexity Hypothesis*, Study 2), independent two-sample t-tests will be used to compare change scores between conditions (i.e., Simple/Complex). Change scores will be based on T2 – T1 for the Immediate ASSIST group and T3 – T2 for the Delayed ASSIST group. Separate linear models will be fitted by adjusting for potential effect of ASSIST delivery time (Immediate/Delayed) to re-assess the effect of complexity.

To address the effect of lexicity (*Word vs. Nonword Hypothesis*, Study 3), independent two-sample t-tests will be used to compare change scores between conditions (i.e., Word/Nonword). Change scores will be based on T2 – T1 for the Immediate ASSIST group and T3 – T2 for the Delayed ASSIST group. Separate linear models will be fitted by adjusting for potential effect of ASSIST delivery time (Immediate/Delayed) to re-assess the effect of lexicity.

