### Statistical Design and Analysis Plan

Descriptive statistics (e.g., mean, median, standard deviation, skewness, and frequencies) will be computed for all variables to ensure data quality and evaluate assumptions of statistical tests. We will compare the pre-treatment performance between the immediate treatment groups and the control groups of each study to assess the success of randomization in producing two comparable groups. Although we do not expect any imbalance between the immediate treatment and control groups, we will adjust for any differences in our subsequent analyses to be sure any treatment effect is not due to potential confounds. For all analyses described in this study, we will use Statistical Analysis Software (SAS, v9.4, Cary, N.C.), with two-sided tests under presumed significant level of 0.05.

To address Specific Aim 1, independent two-sample t-tests will be used to compare gain scores (T1 to T2) from each proximal outcome measure, i.e., *speech accuracy of treated items* and *speech accuracy of generalization items*, between immediate treatment groups and the control groups with combined Studies 1 and 2 (**Figure 3**). A separate linear model will be fitted by adjusting for potential effect of study (Study 1/Study 2) to re-assess the initial efficacy of ASSIST.

To address Specific Aims 2a and 2b, independent two-sample t-tests will be used to compare gain scores from each proximal outcome measure, i.e., *speech accuracy of treated items* and *speech accuracy of generalization items*, between conditions (i.e., simple/complex, word/nonword). Gain scores will be based on T1 to T2 for Immediate groups and T2 to T3 for Delayed groups. Separate linear models will be fitted by adjusting for potential effect of ASSIST delivery time (Immediate/Delayed) to re-assess the parameters of *complexity* and *lexicality*.

To address Specific Aim 2c, independent two-sample t-tests will be used to compare gain scores (T1 to T3) from each proximal outcome measure, i.e., *speech accuracy of treated items* and *speech accuracy of generalization items*, between massed ASSIST group and the distributed ASSIST group. Because the Massed ASSIST group combines both Immediate Massed and Delayed Massed groups, no additional models will be fitted by adjusting potential effect of ASSIST delivery time (Immediate/Delayed) to re-assess the parameter of *intensity*.

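### Study 1's primary score on treated items has no stated item set for delayed controls at T2, and in both arms the treated subset is settled by performance after randomization

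*Protocol*

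**What the plan says.** **Endpoint and contrast.** Protocol Section 9.4.2 states: "The primary endpoint measure is change score from 1 week pre to 1 week post treatment". On how the score is built it says: "Mean across the data analysts for each target is then used to compute the mean across treated targets (primary endpoint". This is done at each of T1, T2 and T3. For Study 1 the T2 – T1 change is compared "between the Immediate ASSIST group and the No ASSIST delayed control group".

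**How items become treated.** Section 6.1.1.1.3 gives each child 30 candidate items. It says "In any session, children practice only 4 targets to maximize practice amount for those targets", and "When all frames for a target are mastered, a new target is introduced". It also lists the target among the elements varied by step-up and step-down criteria. Section 6.2.1 says the session tracking sheets inform decisions to change targets.

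**What is fixed beforehand.** Section 6.3 says "We create target sets before randomization to avoid bias". No order of introduction and no number of treated items is stated.

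**The full set.** Section 8.1.2 defines SE-1 as "Perceptual accuracy of the full 30-item set of potential targets".

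**SAP.** The Statistical Design and Analysis Plan compares T1-to-T2 gains on treated items and on "speech accuracy of generalization items". It does not define the second group of items and does not mention the full 30-item score.

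**The concern.** Randomization protects a comparison when the outcome is measured in the same way in both arms. Here the outcome is a mean over a subset of items, and the plan does not say how that subset is fixed for controls. Section 9.4.2 describes a change from before to after treatment, but a control's T2 visit comes before treatment.

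The obvious retrospective reading is to score each control on the items practised later, in weeks 5–6. The Immediate arm's items would then be settled by events inside the T1–T2 outcome window, and the controls' items by events after it. If getting an item into treatment is related to how that item was changing anyway, the two arms' change scores can differ with no treatment effect.

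Even without bias, two analysts could read the text differently (items treated later, a pre-assigned subset, or all 30) and obtain different primary results from the same data. The SAP's split into treated and generalization items has the same gap for controls.

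**Working it through.** **1. The plan's own power figure.** Inputs from Protocol Section 9.2: n = 20 per arm, d = 0.909, two-sided alpha 0.05, two-sample t-test. Noncentrality = d × √(n/2) = 0.909 × √10 = 2.87, with 38 degrees of freedom. The noncentral t distribution gives 79.99%, against the stated 80%. The power calculation is sound for a well-defined treated-item score, so the fault is in the definition.

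**2. When each arm's treated subset is settled.**

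| | Immediate | Delayed |
|---|---|---|
| Pool of 30 items | before randomization | before randomization |
| Outcome window | T1 (week 1) to T2 (week 4) | T1 (week 1) to T2 (week 4) |
| ASSIST given | weeks 2–3 | weeks 5–6 |
| Treated subset settled | inside the window | after the window |

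The pool is protected and the subset is not. With 4 targets per session and 30 in the pool, the number treated, k, lies between 4 and 30. The documents narrow it no further.

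**3. What a dependence would do (illustration on assumed values, no treatment effect).** Assume a 0–1 accuracy scale, persistent item-level change with SD 0.25, child-level SD 0.10, probe noise SD 0.20, and k = 10. Let w be the correlation between an item's selection in the Immediate arm and its own underlying T1–T2 change, with control items chosen independently of change. Then

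false difference ≈ w × 0.25 × i(k),

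where i(k) is the expected mean of the top k of 30 standard normal values; i(10) = 1.06. At w = 0.3 this is 0.3 × 0.25 × 1.06 = 0.080, or 8.0 points. Simulation (4,000 trials of 20 per arm) gave:

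| Item sets | False difference (points) | Type I error |
|---|---|---|
| All 30 in both arms | 0.0 | 5.5% |
| Random subset in both arms | −0.1 | 4.9% |
| w = 0.1 | 2.4 | 8% |
| w = 0.2 | 5.2 | 17% |
| w = 0.3 | 7.9 | 35% |
| w = 0.5 | 13.1 | 75% |

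Selection toward slowly changing items gives differences of the same size with the opposite sign. At w = 0.3, type I error falls from 38% with 4 items treated to 5.6% with 28 of 30. None of the SDs, w or k is in the documents. The table shows how the bias behaves and does not estimate its size in this trial.

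**4. What the remedies cost in power.** Assume no generalization to unpractised items and an unchanged SD. If a fraction f of the scored items is practised, d becomes 0.909 × f, with 20 per arm:

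| f | As items out of 30 | d | Power |
|---|---|---|---|
| 1.00 | 30 | 0.909 | 80.0% |
| 0.80 | 24 | 0.727 | 61.1% |
| 0.67 | 20 | 0.606 | 46.3% |
| 0.33 | 10 | 0.303 | 15.4% |

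The same fractions apply to a list of k items of which only some are reached. Generalization, or a smaller SD from averaging more items, would raise these figures.

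**The case against.** The strongest reply is that the gap is narrow. Controls repeat the items at T1, T2 and T3 (Protocol Section 1.3), and all children are due to receive ASSIST eventually. A T2 – T1 score on later-treated items can therefore be computed. A reader might infer that the endpoint does not exist for controls, and the documents do not support that: it is undefined, not impossible to compute.

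A reader might also infer a large regression-to-the-mean artefact, with clinicians picking items that looked weak at the latest probe. The documents do not support that either. Section 7.2.2 says the accuracy judgments are completed only after each camp ends, Section 6.3 has them made by assistants outside the camp, and Section 6.1.1.1.3 ties adaptation to performance within sessions. Nothing shows that clinicians have probe scores to select on.

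Three further replies carry weight. Mastery mainly governs how many items enter treatment, and no passage says the next item is picked by its accuracy. The Clinician Manual, which was not available for this review, may set an order. And SE-1, which Section 3 lists under the primary objective, already gives a comparison free of item selection.

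What survives is the absence of a rule for controls, together with a post-randomization subset settled on a different timetable in each arm. A fixed pool does not fix the subset. A clean secondary endpoint does not repair the primary one, and the SAP omits it.

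**Conclusion.** The point holds as a gap in the definition of the sole primary endpoint of the primary study, with a possible bias of unknown size and sign. It rests on two things: the documents give no rule for the controls' items, and treated items emerge from performance after allocation. The bias is zero if order of introduction is unrelated to the items' accuracy or change, and small if nearly all 30 items are treated. The documents settle neither condition, so no range in percentage points can be attached to this trial. The stated sample size and power are not in error. The timing mismatch is specific to Study 1; in Studies 2 to 4 every child has been treated by the assessment used. It should be settled before the primary analysis because one rule for both arms removes the problem cheaply.

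**What to change.** 1. When each child's 30-item set is created, before allocation is revealed, record an ordered list by the same rule for every child, for example a random order. In Cycle 2, order the word–nonword pairs once and use the version that matches the allocated condition.
2. In Protocol Sections 8.1.2 and 9.4.2 and in the SAP, define the primary item set in both arms as the first k positions, scored whether or not each item was reached. State k in the SAP.
3. Report the items actually practised as a supportive analysis.
4. Add the full 30-item endpoint (SE-1) to the SAP and reconcile it with the generalization items named there. Keep SE-1 secondary unless power is re-derived.

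This is a scoring rule and places no requirement on how clinicians sequence targets.

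**Cost.** A short paragraph in each document and one list per child. The real price is dilution when children do not reach all k items or are treated out of the listed order. On the assumptions above, practising 80% of the listed items leaves about 61% power, so k should be no larger than most children are expected to reach. Making the 30-item set primary instead would remove the selection but costs more: about 46% power if 20 of 30 items are treated.

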4 STUDY DESIGN

4.1 OVERALL DESIGN

4.1.1 OVERVIEW

Below is a reminder of the design of the four RCTs in this study (3 cycles plus 1 study combined across Cycles 1 and 2). Dashed box indicates the primary study (Study 1: ASSIST vs. Delayed Control).

Cycle 1 (Summer 1): COMPLEXITY (simple vs. complex real words).								
Group	Condition	wk1	wk2	wk3	wk4	wk5	wk6	wk7
Immediate ASSIST	Simple	T1	8 hrs	8 hrs	T2			T3
	Complex		8 hrs	8 hrs				
Delayed ASSIST	Simple					8 hrs	8 hrs	
	Complex					8 hrs	8 hrs	

Cycle 2 (Summer 2): LEXICALITY (words vs. nonwords).								
Group	Condition	wk1	wk2	wk3	wk4	wk5	wk6	wk7
Immediate ASSIST	Real	T1	8 hrs	8 hrs	T2			T3
	Nonsense		8 hrs	8 hrs				
Delayed ASSIST	Real					8 hrs	8 hrs	
	Nonsense					8 hrs	8 hrs	

Cycle 3 (Summer 3): INTENSITY (massed vs. distributed treatment).								
Group	Condition	wk1	wk2	wk3	wk4	wk5	wk6	wk7
Massed ASSIST	Immediate	T1	8 hrs	8 hrs	T2			T3
	Delayed					8 hrs	8 hrs	
Distributed ASSIST	Distributed		4 hrs	4hrs		4 hrs	4 hrs	

Given the interwoven design (see **Section 1.2, Schema**, figure repeated above), in both Cycles 1 and 2, children are allocated with equal probability to one of four groups (Immediate Simple/Word, Immediate Complex/Nonword, Delayed Simple/Word, Delayed Complex/Nonword) (5:5:5:5). In Cycle 3, children are allocated to one of 3 groups (Distributed vs. Massed Immediate vs. Massed Delayed) to such that children have equal probability to receive Massed or Distributed ASSIST (5:5:10).

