9.2 SAMPLE SIZE DETERMINATION

As a Phase 1 trial of a novel treatment, this study is not powered to detect a definitive effect. Instead, realistic sample sizes for a summer camp at a single site were used to estimate effect sizes and sample sizes to test the hypotheses described in the previous section (**Section 9.1, Statistical Hypotheses**). Findings from this trial will inform effect size estimates to determine sample sizes to power subsequent Phase 2 and Phase 3 trials and determine the need for multisite trials. Estimates below are for the primary endpoint of perceptual speech accuracy of treated targets, computed using G*Power (Faul et al., 2007); no power estimates were computed for secondary outcome measures.

For the primary endpoint of Study 1 (perceptual speech accuracy) to test the primary hypothesis (*ASSIST Hypothesis*), with a sample size of 40 children (n=20 per condition, ASSIST vs. No ASSIST), $\alpha = 0.05$ (two-tailed), we expect to have at least 80% power to detect an ASSIST treatment effect size (mean difference between groups over the study period, divided by the pooled standard deviation) of 0.909 using a two-sample t-test. The only prior randomized controlled trial for CAS (Murray et al., 2015), with 26 children

enrolled, reported effect sizes of 1.312 and 2.162 with only 12 hours of treatment (two different treatments), suggesting that the present study will have sufficient power to detect effects. See **Table 2** below for estimates of remaining power with different numbers of participants (e.g., in case of under enrollment, attrition).

Table 2. Estimated power to detect effect size of 0.909 for Study 1.

Total N	n per group	Statistical power
40	20	80%
38	19	77%
36	18	75%
34	17	72%
32	16	70%
30	15	67%

For Studies 2-4, with sample sizes of 20 children per study ($n=10$ per condition), $\alpha = 0.05$ (two-tailed), we expect to have at least 80% power to detect condition/intensity treatment effect sizes of 1.325 using a two-sample t-test. See **Table 3** below for estimates of remaining power with different numbers of participants (e.g., in case of under enrollment, attrition).

Table 3. Estimated power to detect effect size of 1.325 for Studies 2-4.

Total N	n per group	Statistical power
20	10	80%
18	9	75%
16	8	69%
14	7	62%
12	6	54%
10	5	45%

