9.4 STATISTICAL ANALYSES

9.4.1 GENERAL APPROACH

Descriptive statistics (e.g., mean, median, standard deviation, skewness, and frequencies) will be computed for all variables to ensure data quality and evaluate assumptions of statistical tests. We will

compare the pre-treatment performance between groups (ASSIST/No-ASSIST, Simple/Complex, Word/Nonword, Massed/Distributed) to assess the success of randomization in producing two comparable groups. Although we do not expect any imbalances between groups, we will adjust for any differences in our subsequent analyses to be sure any treatment effect is not due to potential confounds. For all analyses, we will use Statistical Analysis Software (SAS, v9.4, Cary, N.C.), with two-sided tests under presumed significant level of 0.05.

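### Study 1's planned tests leave out the randomised practice condition, so any Simple/Complex or Word/Nonword difference in the treated arm widens the confidence interval and makes the test conservative

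*Protocol*

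**What the plan says.** Protocol 4.1.1 gives the randomised structure of Cycles 1 and 2: "children are allocated with equal probability to one of four groups (Immediate Simple/Word, Immediate Complex/Nonword, Delayed Simple/Word, Delayed Complex/Nonword) (5:5:5:5"). At T2 the Immediate arm therefore holds 5 Simple and 5 Complex children from Cycle 1, and 5 Word and 5 Nonword children from Cycle 2. These are two randomised pairs, one per cycle, and not a four-way randomisation.

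For Study 1, Protocol 9.4.2 states that "independent two-sample t-tests will be used to compare change scores (T2 – T1) between the Immediate ASSIST group and the No ASSIST delayed control group". The supporting analysis is: "A separate linear model will be fitted by adjusting for potential effect of study (Cycle 1/Cycle 2) to re-assess the initial efficacy of ASSIST". The SAP's Aim 1 paragraph has the same model, labelling the two cycles as studies: "A separate linear model will be fitted by adjusting for potential effect of study (Study 1/Study 2) to re-assess the initial efficacy of ASSIST".

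The other adjustments named are for baseline imbalance (Protocol 9.4.1 and 9.4.5) and sex (9.4.7). For Studies 2 and 3, by contrast, 9.4.2 does add models that adjust for the other randomised factor, delivery time.

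Protocol 9.2 plans Study 1 "with a sample size of 40 children (n=20 per condition, ASSIST vs. No ASSIST") to detect an "effect size (mean difference between groups over the study period, divided by the pooled standard deviation) of 0.909 using a two-sample t-test". For the condition comparisons it says "we expect to have at least 80% power to detect condition/intensity treatment effect sizes of 1.325 using a two-sample t-test". Protocol 4.2 says that randomising conditions within phase is meant to show how robust ASSIST is across conditions.

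**The concern.** Condition is a design factor with cell sizes fixed by the randomisation. If Simple and Complex practice (or Word and Nonword targets) produce different gains, the treated children in a cycle differ systematically by condition. With fixed cell sizes, that difference adds nothing to the true uncertainty of the Immediate arm's mean. The t-test still counts it as residual variation. The Cycle term does not remove it, because the difference lies within each cycle and only among treated children.

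At stake is efficiency in the primary comparison of a 40-child trial. Power falls and the interval widens in just the situation that Studies 2 and 3 look for. The pooled SD, which the plan uses to standardise its effect size, also carries the spread between conditions.

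**Working it through.** **Inputs.** 20 per arm and effect 0.909 (Protocol 9.2); two-sided 0.05 (9.4.1); 5 children per cell (4.1.1). Assumed: within-cell SD 1, no condition effect in untreated children at T2, and a condition difference δ between 0 and 1.325 within-cell SD. The documents give no expected δ. The 1.325 is the difference detectable with 10 per group.

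**The plan's own figure.** The standard error is √(2/20) = 0.316, so the noncentrality is 0.909/0.316 = 2.87. With 38 df the noncentral t gives 79.99% power, against the stated 80%.

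**Residual inflation.** With condition means at ±δ/2 in each cycle, the 20 treated children add 20 × (δ/2)² = 5δ² to the residual sum of squares. Hence

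E[pooled variance] = 1 + 5δ²/38.

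At δ = 0.5 the SD factor is √(1 + 1.25/38) = 1.016. At δ = 1.325 in both cycles it is √(1 + 8.778/38) = 1.11. In one cycle only it is √(1 + 4.389/38) = 1.056.

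**Condition-adjusted model.** Change (T2 − T1) on phase, Cycle, and one condition contrast per cycle for treated children has 5 parameters, so 40 − 5 = 35 df. Its residual SD is the within-cell SD and its noncentrality stays at 2.87. Power is 79.8% at every δ.

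**Power at a mean effect of 0.909** (t-test and Cycle-only model simulated, 8 cells of 5):

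| δ (within-cell SD) | t-test | Cycle-only | Condition-adjusted |
|---|---|---|---|
| 0 | 80% | 80% | 80% |
| 0.5, both cycles | 79% | 79% | 80% |
| 0.8, both cycles | 78% | 78% | 80% |
| 1.325, one cycle | 77% | 77% (76.4–76.6) | 80% |
| 1.325, both cycles | 73% | 73% | 80% |

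The Cycle-only model recovers none of the loss.

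**Interval and error rate at δ = 1.325 in both cycles.** The t-test's mean standard error is 0.349 against a true 0.316. Its 95% interval is about 2 × 2.024 × 0.349 = 1.41 wide, against 2 × 2.030 × 0.314 = 1.28 for the adjusted model. Coverage is 97% against 95%. With a zero average effect the t-test rejects about 3% of the time instead of 5%.

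**On the plan's scale.** If 0.909 is in pooled SDs, as 9.2 defines it, the mean difference at δ = 1.325 is 0.909 × 1.11 = 1.01 within-cell SD. Power is then 82% for the t-test and 87% for the adjusted model.

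**Unequal cells, δ = 0.** Suppose 34 children remain, with treated cells 5, 3, 5, 3 and control cells 5, 4, 4, 5. The variance of the adjusted estimate is (1/16)(1/5 + 1/3 + 1/5 + 1/3) + 1/18 = 0.122, against 1/16 + 1/18 = 0.118 for the t-test. Power is 71% (29 df) against 73% (32 df). Clearly unequal patterns cost about 1 to 3 points. The most lopsided one tried (treated 5, 2, 5, 3; control 5, 5, 4, 5) cost nearly 4.

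**The case against.** The strongest reply is that pooling is deliberate and valid. Protocol 4.2 wants the effect across conditions, and with equal cells the t-test estimates that average without bias. Its error is on the safe side, and the trial says it is not powered for a definitive effect. All of this stands. The adjusted model targets the same average, so the issue is precision only.

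The size of the loss also depends on assumptions. The condition hypotheses compete in direction and no difference is predicted, so 1.325 in both cycles is an upper scenario. At 0.5 SD the gain is under 1 point. The 0.909 is itself the detectable minimum. With the smaller of the two earlier effect sizes cited in 9.2, 1.312, power is about 97% against 98% even at δ = 1.325. This stands, and it limits the point.

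Three stronger readings might be inferred, and the documents do not support them:

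- **That the stated 80% is wrong.** It reproduces exactly, and 9.2 defines the effect in pooled SDs, which already contain the spread between conditions.
- **That the Study 1 test must be replaced by a model saturated in all eight cells.** That model spends 6 df, some of them on condition terms in untreated children, and loses more power when cells are unequal.
- **That a later trial would be mis-sized.** At δ = 1.325 the pooled effect falls to 0.909/√(1 + 1.325²/8) = 0.82, which needs 25 rather than 20 per arm. But a trial of one condition would use that condition's own effect, here 0.909 ± 0.66, or 1.57 and 0.25. Studies 2 and 3 compare the conditions directly.

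**Conclusion.** The point holds as a modest efficiency and reporting improvement, not as a validity failure. Neither planned Study 1 analysis contains condition, and the Cycle term cannot stand in for it. The loss against a condition-adjusted model is nil if conditions do not differ, about 1 point at 0.5 SD, 2 at 0.8, 3 at 1.325 in one cycle, and 6 to 7 at 1.325 in both. In that last case the interval is about 11% too wide.

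These figures rest on a within-cell SD of 1, a mean effect of 0.909 on that scale, complete cells of 5, and no condition effect before treatment. The statements that the estimate is unbiased and the test conservative also assume equal cells.

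**What to change.** In Protocol 9.4.2 and the SAP's Aim 1 paragraph, extend the existing Cycle-adjusted model to

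change (T2 − T1) = phase + Cycle + condition within cycle for the treated arm.

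Code Cycle as ±1/2. Code Simple/Complex as ±1/2 for Immediate children in Cycle 1 and 0 for everyone else, and Word/Nonword likewise in Cycle 2. The phase coefficient then weights the two conditions of a cycle equally, and with complete cells it equals the t-test's mean difference. Report it as the ASSIST effect averaged over conditions. Give the within-cell residual SD beside the pooled SD for Phase 2 and 3 planning. The t-test can stay as planned.

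The cost is wording in two documents and a few lines of SAS, with no new data or children. The model uses 3 df more than the t-test and 2 more than the Cycle model. That costs about 0.2 to 0.3 of a power point with complete data and no condition effect, and about 1 to 3 points if attrition leaves clearly unequal cells (nearly 4 in the extreme pattern shown).
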